Privacy, Data Storage, & Confidentiality: The following precautions will protect the privacy of participants and maintain confidentiality of research data: (1) All staff will be well trained in confidentiality and data security procedures. (2) Privacy will be maintained by conducting all study procedures in closed rooms. (3) Each participant will be assigned a unique study ID number, and all data will be de-identified and coded with ID numbers only. The key linking participant names and ID numbers will be stored in a separate password protected document on Duke OIT approved servers and electronic storage locations, and only essential study staff will have access to it. (4) Documents such as informed consents, copies of laboratory results, and outside medical records obtained as part of the study will be securely stored in locked file cabinets in locked offices and in password protected documents on password protected computers and secure servers. Access to data storage areas and computers will be restricted to designated key personnel. (5) Analysis will occur on de-identified data only. (6) Data will only be stored for as long as necessary to complete the study, and for adherence to university, hospital, and federal regulations.

The risk of loss of confidentiality is inherent in all research studies, and a statement to this effect will be included in the informed consent. Confidentiality will be assured by a number of procedures. First, all staff receive careful training in the importance of participant confidentiality, the separation of data from participant's tracking information, and the use of locked offices, file cabinets, and computer accounts to prevent unauthorized access to the data or identifying information. Second, all study data will be treated confidentially. All questionnaires, and forms will be identified by participant ID (PID/SID) only. No identifying information will be included in the analytical database, nor in any presentations nor publication. All study materials and surveys will be maintained in locked filing cabinets in a secured office at all times. All records with personally-identifying information will be kept in a locked, limited access area (such as a locked file cabinet) available only to site principal investigators and designated study personnel.

REFERENCES:

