Aim 1. Identify the pathology, structural cell profile (airway fibroblast and epithelial cell) and redox status corresponding to regional areas of fixed and reversible post-bronchodilator defects (BD) in obese asthmatics.

We hypothesize that post-BD fixed defects identified on ¹²⁹XeMRI correspond to sites of increased oxidant stress and airway remodeling and fibrosis. We will use ¹²⁹XeMR imaging to guide bronchoscopy sampling of airways in both BD fixed and BD reversible ventilation defects. We will relate the contribution of the oxidant milieu, structural cell phenotypes and histopathologic composition of airways to changes in ventilation defects observed on ¹²⁹XeMRI.

Aim 2. Define the cellular requirement for redox-mediated TGF-β signaling between airway epithelial cells and fibroblasts driving regional remodeling in obese asthma. We hypothesize that regions of fixed defects on ¹²⁹XeMRI are composed of airway fibroblasts that are more proliferative, invasive and fibrogenic than fibroblasts in BD reversible defects and respond to the increased oxidative milieu and TGF-β signaling. We will assess epithelial cell signaling, airway fibroblast migration/invasiveness, proliferation and extracellular matrix (ECM) protein secretion with *ex vivo* cell culture models. These assays will establish significant associations between airway epithelial signaling and fibroblast function, changes in airway ventilation, and asthma endotypes.

Aim 3 Define regional differences of spatial interactions of mesenchymal cells with epithelial cells in the airway submucosa.

3A - Determine how transcriptional profiles change between lean vs obese asthma and controls;

3B - Determine how transcriptional profiles change in BD fixed vs responsive regions in obese asthma.

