We hypothesize that local gene expression changes and cell signaling among both structural cells and immune cells in airway tissue contributes to airway remodeling in asthma patients with obesity. We plan to utilize spatial transcriptomics techniques to analyze endobronchial tissue samples isolated from asthma and non-asthma participants with and without obesity to compare specific airway tissue gene expression patterns in asthma vs non-asthma participants, participants with obesity vs non-obesity, and combined conditions. These gene expression patterns will be localized to pathologic features of asthma and obesity, including accumulation of submucosal eosinophils, fibrosis, smooth muscle and basement membrane thickening, etc in the tissue sections.

We are collaborating with [name] at Northwestern and Dr's. [name] and [name] (Duke pathologists) for this aim. Cryopreserved airway tissues from deidentified participants will be used for **Aim 3A** and include tables containing the demographics, physiology, FeNO, ACQ and atopy status. Endobronchial biopsies obtained from participants in this study will be deidentified and included in **Aim 3B**.

Purpose of the Study:

The proposed study will determine if sites of abnormal ventilation on $^{129}\text{XeMRI}$ represent areas of airway remodeling and fibrosis enriched with fibroblasts that are invasive, proliferative and fibrogenic. We hypothesize that regional alterations in oxidant stress drive the production of transforming growth factor-beta (TGF- β) which directs pro-remodeling fibroblast functions. We predict that $^{129}\text{XeMRI}$ will be a sensitive and specific biomarker of airway remodeling and fibrosis in obese subjects with asthma.

Primary outcomes:

- We will identify the pathology, structural cell profile (airway fibroblast and epithelial cell) and redox status corresponding to regional areas of fixed and reversible post-bronchodilator defects (BD) in obese asthmatics;
- We will define the cellular requirement for redox-mediated TGF- β signaling between airway epithelial cells and fibroblasts driving regional remodeling in obese asthma;
- We will develop non-invasive 3D imaging techniques to assess airway regional remodeling in obese asthma.

Secondary outcomes:

- We predict that $^{129}\text{XeMRI}$ will be a sensitive biomarker of asthma control and severity of disease.

BACKGROUND & SIGNIFICANCE:

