Obese asthma. Obese asthma is a major public health concern. The prevalence of obesity continues to rise at an alarming rate and has reached epidemic proportions over the past several decades. Obesity is a risk factor for the development of asthma and is associated with approximately 250,000 cases per year in the U.S. ¹. In patients with established asthma, obesity is associated with increased risk for exacerbations, worse respiratory symptoms and poor control ^{2,3}. Obesity and weight gain are associated with increased asthma severity and a nearly 5-fold risk of hospitalization ⁴. *This is a major public health concern, given that the Centers for Disease Control has estimated that 38.8% of asthmatics are obese.*

[figure not shown]
Obese asthma is broadly categorized into two distinct endotypes, early vs. late onset disease. Early onset obese asthma is defined as being diagnosed at <12 years of age, associated with type 2 (T2) high disease, an allergic phenotype, and the development of obesity as a consequence of asthma. Late-onset obese asthma occurs after 12 years of age or in adulthood ⁵ and is associated with the development of asthma subsequent to obesity ⁶. In early onset asthma, obesity contributes to disease severity and is associated with an increased incidence of fixed airway obstruction ⁷; this fixed obstruction is also referred to as airway remodeling and/or fibrosis (structural changes of the airway wall), and manifests as bronchodilator non-responsiveness. In contrast, the late onset obese asthmatic is a common and unique clinical phenotype that is not defined by T2-related airway inflammation. Despite having relatively preserved lung function and lower fractional exhaled nitric oxide (FeNO) levels, cluster analyses show that those asthmatics characterized by body mass index (BMI) >30 kg/m² with late onset disease have a high symptom burden and high utilization of healthcare resources ⁸⁻¹⁰. New biologics targeting T2 high asthma are less effective in obese asthmatics compared to lean patients and are not efficacious in non-T2 disease ^{11,12}. Therefore, we need to better understand how asthma differs in the obese population. Only with such understanding will it become possible to develop effective therapies that benefit these patients.

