Data analysis will be performed using a suite of python-based tools suitable for handling large-scale datasets (>5M cells), including scVI-tools, SquidPy and CellCharter. Briefly, after data QC and filtering out cells with low number of transcripts, we will integrate data from all samples together, and perform clustering, similar to single-cell RNA-seq analysis. The resulting cell clusters will be annotated using manual review of marker genes or label transfer from single-cell RNA-seq atlases using transfer learning tool scArches (part of scVI-tools and CellCharter), and these clusters will be projected back into spatial context. We will compare the relative abundance and absolute density of specific cell types between groups. We will also extract additional features, such as cell size or morphological characteristics. We will use CellCharter to perform unbiased identification of spatial neighborhoods and test their association between groups with adjustment for demographic covariates.

DATA & SAFETY MONITORING:

Patient safety and the integrity of the study will be monitored by an appointed university DSMB via review of adverse events and other safety parameters at their regularly scheduled meetings.

Data Storage and Handling and Record Keeping:

Any CRFs will be entered directly into REDCap by the study coordinator, with the support of Duke's office of clinical research.

Data will be captured in REDCap, except for patient consent forms, and AE/SAE forms, which will be on case report forms (CRFs) collected by the coordinators. REDCap is a software tool that does not require client local software and can be accessed from anywhere on the Internet and is secured on a Duke Health Technology Services (DHTS) server. All collected data are backed up daily, both on the local server and by the DHTS enterprise backup system.

Source Documents and Records Retention. Original source documents (consents) for study participants will be maintained at the study site at the Duke Asthma Allergy Airway Center research offices in a badge accessed office in locked cabinets and will be accessible only to the study staff.

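### Aim 3A tissue comes with FeNO and atopy data, but the planned adjustment is demographic only, so a lean-obese asthma difference cannot be separated from any difference in type 2 mix

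*Combined protocol and SAP*

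**What the plan says.** The Specific Aims define Aim 3A as follows: "Determine how transcriptional profiles change between lean vs obese asthma and controls". The paragraph after Aim 3B adds contrasts of "participants with obesity vs non-obesity, and combined conditions" and lists submucosal eosinophils among the features to which expression will be localized.

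On the source of tissue: "Cryopreserved airway tissues from deidentified participants will be used for" Aim 3A, and these tissues "include tables containing the demographics, physiology, FeNO, ACQ and atopy status". No group sizes, selection rule or matching rule are given. The study's own asthma cohort requires a BMI of at least 30 kg/m², so the lean donors must come from elsewhere.

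The analysis is in the last paragraph of Data Analysis & Statistical Considerations, the one on spatial tools. For cell types: "We will compare the relative abundance and absolute density of specific cell types between groups", with no adjustment stated. For spatial neighborhoods the plan will "test their association between groups with adjustment for demographic covariates". FeNO and atopy are not mentioned there, and no other section assigns them to adjustment, stratification or matching in Aim 3A.

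Background & Significance (Obese asthma) describes early-onset obese asthma as T2 high and allergic. It calls late-onset obese asthma a "unique clinical phenotype that is not defined by T2-related airway inflammation" and says of those patients: "Despite having relatively preserved lung function and lower fractional exhaled nitric oxide (FeNO) levels".

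**The concern.** The groups in Aim 3A are observational, and the tissue was not collected to be balanced on T2 status. By the protocol's own account, T2 status varies with the kind of obese asthma a donor has. It also bears on the readouts of interest. The background on airway remodeling links IL-13 in T2-high disease to fibroblast invasion through TGF-β1, and the analysis section links TGF-β1 to eosinophil burden and severity in T2-high disease. T2 status could therefore move the epithelial, mesenchymal and eosinophil signals that Aim 3 examines.

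Age, sex and race do not stand in for T2 status. If the lean and obese donors differ in T2 mix, the planned comparison will show that difference together with any difference due to obesity, and nothing in the plan would let a reader tell the two apart, although the variables needed for a first attempt are supplied with the tissue.

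**Working it through.** **Check against the text.** The variables supplied are demographics, physiology, FeNO, ACQ and atopy. The variables used for adjustment are demographics for the neighborhood test, and none stated for abundance and density. The gap is confirmed and is wider for abundance and density. The spatial paragraph does not separate 3A from 3B. The fixed-versus-responsive contrast in 3B can be made within a patient, where patient-level FeNO and atopy cancel, so the point concerns 3A.

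**Size.** The plan states no sample size, effect size or error rate for Aim 3A, so there is no figure to reproduce. All inputs below are assumptions: T2-high shares, a T2 effect of 1 or 2 SD (SD within T2 stratum), 10 or 20 donors per group, and a two-sided 5% test. The true lean-obese difference net of T2 is set to zero.

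Shift in the lean-obese difference = T2 effect × (lean T2-high share − obese T2-high share).
Example: 1 × (0.70 − 0.40) = 0.30 SD; 2 × 0.30 = 0.60 SD.

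The table shows how often a difference is declared without T2 adjustment (simulation, 4,000 runs per scenario, donors sampled at the stated shares; ranges cover repeated runs).

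| T2-high, lean v obese | Shift for 1 / 2 SD | 10 per group, 1 / 2 SD | 20 per group, 1 / 2 SD |
|---|---|---|---|
| equal | 0 / 0 | no excess | no excess |
| 60% v 50% | 0.10 / 0.20 SD | 5-8% in all four cells | (same) |
| 70% v 40% | 0.30 / 0.60 SD | 9% / 16% | 14% / 26-27% |
| 80% v 30% | 0.50 / 1.00 SD | 17-18% / 37% | 28-31% / 65% |

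With the shares held exactly fixed rather than sampled, the rates are generally lower (70% v 40%: 6-7% with 10 per group, 11-19% with 20). The shift is the same.

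**What adjustment achieves.** With perfectly measured T2 status in the model, the shift is about zero and the rate about 5%. FeNO and atopy are not perfect measures. Take a binary marker with 80% sensitivity and specificity (assumed), at 70% v 40%:

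- Marker-positive shares: 0.2 + 0.6 × 0.70 = 0.62 and 0.2 + 0.6 × 0.40 = 0.44; difference 0.18.
- Within-group covariance of T2 and marker: 0.6 × average of (0.21, 0.24) = 0.135.
- Within-group variance of the marker: average of (0.62 × 0.38, 0.44 × 0.56) = 0.241.
- Slope of T2 on the marker: 0.135 / 0.241 = 0.56.
- Share difference left after adjustment: 0.30 − 0.56 × 0.18 = 0.20.
- For a 2 SD T2 effect: 2 × 0.20 = 0.40 SD, down from 0.60 SD.

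In simulation this leaves a rate of about 10% with 10 per group and 16-17% with 20. Adjustment removes part of the shift, not all of it.

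**The case against.** The strongest reply is that the plan never claims an obesity effect net of T2. Aim 3A asks how profiles differ between groups, and the analysis tests association between groups. On that descriptive reading, a different T2 mix is part of the answer, and the rates above are not false positives. This stands: a reader might infer that the plan will wrongly credit T2 differences to obesity, but no section commits to that attribution. What remains is that the reported difference could not be interpreted either way.

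A reader might also infer from the background that lean and obese donors are known to differ in T2 mix. They are not. That section contrasts early- with late-onset obese asthma and gives no mix for lean asthma, and the composition of the archive is not described. The imbalance is plausible, not shown.

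Third, T2 status may be a mediator. The same section says that late-onset asthma follows obesity, whereas in early-onset disease obesity follows asthma. Adjusting could therefore remove a real obesity effect that acts through T2. This also stands, and it rules out treating the adjusted estimate as the only valid one.

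Fourth, the background on biomarkers says T2 markers predict eosinophilic airway inflammation poorly in T2-high obese asthma, so adjustment will be incomplete. That limits what the second estimate can show, but it is no reason to leave supplied variables unused.

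Finally, the sections will already be examined for submucosal eosinophils, a more direct view of T2 pathology than FeNO. That is localization, however, not adjustment of the group comparison.

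**Conclusion.** The point holds as a gap in the planned analysis. The Aim 3A lean-obese asthma contrast will mix obesity with T2 inflammation to whatever extent the donors' T2 mixes differ, and the plan has no step that separates them or shows whether they differ. The size cannot be stated from the documents: it is zero with equal mixes, small at 60% v 50%, and 0.30 to 1.00 SD across the two larger assumed imbalances and T2 effects of 1 to 2 SD.

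Two stronger conclusions are tempting and not supported. One is that adding FeNO and atopy would restore a 5% error rate; that holds only for perfectly measured T2 status, and the protocol itself doubts the markers. The other is that only differences surviving adjustment are obesity effects; the protocol's own account of late-onset disease makes T2 a possible mediator.

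Severity is minor. Aim 3 is absent from the synopsis aims and from the listed primary and secondary outcomes, so no main conclusion depends on it.

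**What to change.** In the spatial analysis paragraph of Data Analysis & Statistical Considerations, for the Aim 3A asthma contrasts:

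1. Tabulate FeNO and atopy status by group, so that any T2 imbalance is visible.
2. Apply the demographic adjustment to cell-type abundance and density as well as to neighborhoods.
3. Beside each demographic-adjusted estimate, report a second one that also adjusts for log FeNO and atopy, or stratifies by T2 status.
4. Label the first as the overall lean-obese difference and the second as the difference not explained by measured T2 status. State that T2 may be a mediator in late-onset disease and that adjustment is incomplete because the markers are imperfect. Do not add a rule that lets only the second estimate count as an obesity effect.

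The tissue eosinophils already to be localized could support a sensitivity analysis.

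The cost is a wording change and one further model, with no new data. The second model spends about two degrees of freedom and gives wider intervals, which will matter if the groups are small.

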Study Schedule	
Following prescreening for eligibility, participants will provide consent, and undergo a screening visit (V 0) which includes:
 
Screening visit (V 0)
 
 • Urine pregnancy for women of child-bearing potential • Anthropometrics and vital signs • Medical history including current and past medication review • Asthma control questionnaire (ACQ) • Skin allergy testing, • Blood draw for labs: 
 ○ CBC with diff (LAB1748) 4.0 mL ○ fasting blood glucose (LAB81) 4.0 mL ○ total cholesterol (LAB60) 4.5 mL ○ triglycerides (LAB134) 4.5 mL ○ chemistries (LAB15) 4.5 mL, and ○ serum IGE (LAB74) 3.5 mL ○ CPT 8.0 mL ○ Total blood volume = 33 mL • Impulse oscillometry (IOS) measurements • Pulmonary function testing will be performed including: 
 ○ exhaled nitric oxide (FeNO), 
 ▪ May be repeated once if results are high ○ spirometry ○ Lung volumes via body plethysmograph ○ Methacholine challenge 
Visit 1 (1-2 weeks after visit 0)
 
 • Urine pregnancy for women of child-bearing potential • Interim medical history and medications will be reviewed, and any AE's evaluated. • Vital signs • ACQ • The participants will have a standard dose chest CT • Hyperpolarized Xe-MRI performed pre and post bronchodilator. • Approximately 24-hours after MRI, a follow up phone call. 
Visit 2 (1-2 weeks after visit 1)
 
 • Urine pregnancy for women of child-bearing potential • Standard of Care (SOC) Bronchoscopy consent • Vital signs and brief physical exam • Interim medical history and medications will be reviewed, and any AE's evaluated. • The participants will have a bronchoscopy with broncho-alveolar lavage (BAL), brushes and biopsy. 
Visit 3
 
 • A follow up phone call.
----------------	---

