Data Collection	
Data will be captured in REDCap, except for patient consent forms and AE/SAE forms, which will be on case report forms (CRFs) collected by the coordinators. REDCap is a software tool that does not require client local software and can be accessed from anywhere on the Internet and is secured on a Duke Health Technology Services (DHTS) server. Established systems for data entry, verification, and error-checking will be followed.

Schedule of Events:

Week	-1	0	1	1+
Visit number	V0	V1	V2	V3
Study ICF	x			
Bronchoscopy SOC consent			x	
Vital signs	x	x	x	
Baseline medical history, including current and past medication review	x			
Interim medical and medications review and any AE's evaluated		x	x	
Brief physical exam			x	

Week	-1	0	1	1+
Visit number	V0	V1	V2	V3
ACQ	x	x		
Spirometry	x			
Impulse oscillometry (IOS)	x			
FeNo	x			
Lung volumes via body plethysmograph	x			
Methacholine challenge	x			
Blood draw for clinical labs*	x			
Skin Allergen panel	x			
Anthropometrics	x			
Pregnancy test**	x	x	x	
CT Scan		x		
¹²⁹ XeMRI pre and post bronchodilator		x		
Bronchoscopy			x	
Follow-up phone call		X (24 hours after MRI)		X (24 hours after bronchoscopy)

*Clinical labs: CBC with diff (LAB1748) 4.0 mL, fasting blood glucose (LAB81) 4.0 mL, total cholesterol (LAB60) 4.5 mL, triglycerides (LAB134) 4.5 mL, chemistries (LAB15) 4.5 mL, and serum IGE (LAB74) 3.5 mL, CPT 8.0 mL

**for women of child-bearing potential

The **central hypothesis** is that sites of abnormal ventilation on ¹²⁹XeMRI represent areas of airway remodeling and fibrosis and are enriched with fibroblasts that are invasive, proliferative and fibrogenic. We further hypothesize that regional alterations in oxidant stress driving the production of transforming growth factor-beta (TGF-β) direct pro-remodeling fibroblast functions. Lastly, we hypothesize that ¹²⁹XeMRI will be a sensitive and specific biomarker of airway remodeling and fibrosis in obese asthmatics and rat models of obese asthma. By leveraging our excellence in clinical asthma, bronchoscopy, and translational expertise in cell function/signaling and 3D MR imaging in both patients and animal models, we will conduct both *ex vivo* cell-specific mechanistic studies and *in vivo* animal model studies to uncover the mechanisms of molecular and cellular function through the following **Specific Aims**:

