Following Informed Consent, participants will be enrolled and will be assigned a study ID in consecutive order from the assignment log provided record the assignment on the study log. All enrolled participants will then perform:

- Urine pregnancy for women of child-bearing potential
- Anthropometrics and vital signs
- Medical history review (including the following: age of asthma onset, prior hospitalizations, ER visits, steroid use, frequency of asthma exacerbations, antibiotic use, nocturnal awakenings, frequency of SABA use, immune desensitization, current and past medication use, self-described smoking history)
 - Demographics (race, ethnicity, gender, age)
- ACQ
- Skin allergy testing,
- Blood draw for labs:
 - CBC with diff (LAB1748) 4.0 mL
 - fasting blood glucose (LAB81) 4.0 mL
 - total cholesterol (LAB60) 4.5 mL
 - triglycerides (LAB134) 4.5 mL
 - chemistries (LAB15) 4.5 mL
 - serum IGE (LAB74) 3.5 mL
 - CPT 8.0 mL
 - Total blood volume = 33 mL
- IOS
- Pulmonary function testing will be performed including:
 - exhaled nitric oxide (FeNO),
 - May be repeated once if results are high
 - spirometry
 - Lung volumes via body plethysmography
 - Methacholine challenge

Visit 1 – 4 hours (week 0)

- Urine pregnancy for women of child-bearing potential
- Interim medical history and medications will be reviewed, and any AE's evaluated
- Vital signs

- ACQ
- Standard dose chest CT (SDCT)
- Hyperpolarized ^{129}Xe MRI pre and post bronchodilator.
- Participants will receive a follow up phone call approximately 24 hours after the MRI with the coordinator, including a review of interim medical history and medications and any AE's evaluated

Visit 2 – 2 hours (week 1)

- Standard of Care (SOC) Bronchoscopy consent
- Urine pregnancy for women of child-bearing potential
- Vital signs and brief physical exam
- Interim medical history and medications will be reviewed, and any AE's evaluated.
- Bronchoscopy with BAL 90 ml per airway in two airways for a total of 180 ml, and up to 6 brushes per airway (12 total) and endobronchial biopsies per airway segment (up to 12 total).
- Post-procedure observation in the recovery area of 25 minutes to 1 hour.

The participant will not be allowed to proceed with the bronchoscopy visit which includes moderate conscious sedation without an adult that comes with them during the check in process and is available to escort the participant home.

Visit 3 – follow up (1 week after visit 2)

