- Participants will receive a follow up phone call with the coordinator, including a review of interim medical history and medications and any AE's evaluated

Asthma Cohort Inclusion / Exclusion Criteria are as follows:

INCLUSION

1. Adequate completion of informed consent process with written documentation
2. Male and female patients, 18 - 65 years old, inclusive
3. Physician diagnosis of asthma for > 1 year
4. Able to perform reproducible spirometry according to ATS criteria
5. All racial/ethnic backgrounds may participate
6. BMI ≥ 30 kg/m²
7. Regular treatment with ICS or ICS/LABA and/or LAMA combination medication for at least 3 months; on a stable dose for the 4 weeks prior to Visit 0
8. Smoking history <10 pack years and no smoking in the last 3 months
9. Late onset asthma: Age of asthma onset (diagnosis) ≥ 12 years;
 - FeNO < 25 ppb at Visit 0
 - Negative allergen skin test
10. Early onset asthma: Age of asthma onset (diagnosis) <12 years
 - FeNO ≥ 25 ppb at Visit 0
 - Positive allergen skin test
11. Positive Methacholine challenge- Confirmation of asthma: Either (1) 12% or greater bronchodilator response (BDR) in FEV1 to albuterol at Visit 0 OR (2) PC20 methacholine ≤ 16 mg/ml at Visit 0 (historical results from previous studies or documented in clinical records within preceding year are acceptable alternatives) AND/OR Positive PD40 to X5 and R5 on IOS.

EXCLUSION:

1. Respiratory tract infection within the 4 weeks prior to Visit 0
2. Oral or systemic corticosteroid burst (for any indication) within the 4 weeks prior to Visit 0
 - One-time doses, such as intra-articular injections into a shoulder or knee joint, require a 4-week washout prior to Visit 0
3. Asthma-related ER visit within the previous 4 weeks of Visit 0

4. History of ICU admission/intubation due to asthma in the past 1 year
5. Three or more asthma exacerbations requiring treatment with systemic corticosteroids in the past year consistent with severe asthma
6. Asthma exacerbation requiring systemic corticosteroids within the 4 weeks prior to Visit 0
7. Significant concomitant medical illness, including (but not limited to) heart disease, cancer, uncontrolled diabetes, other chronic lung diseases
8. Chronic renal failure (creatinine > 2.0) at Visit 0
9. Positive urine pregnancy test at Visit 0 or at any time during the study
10. Untreated sleep apnea

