- The costs for any care that will be needed to diagnose or treat an incidental finding would not be paid for by this research study. Any additional tests or treatments will be your choice; you or your insurer will be responsible for additional costs.

7. *Bronchoscopy:*

Risks: There is the small risk of bleeding, bronchospasm, irregular heartbeat, shortness of breath, infection or pneumonia in approximately 1-5% of individuals with asthma undergoing bronchoscopy^{47,52}. There is a possibility that bronchospasm can worsen by this procedure. If this occurs, appropriate treatment including albuterol nebulization will be given. If the subject's asthma symptoms continue, the procedure will be terminated, and additional medications will be given if clinically indicated. During the procedure, there may be a temporary drop in oxygen levels. Subjects will be given supplemental oxygen to keep levels normal. If a subject experiences difficulty necessitating continued observation, he/she will be hospitalized. Unstable patients will be transferred to the Medical Intensive Care Unit. Other risks of bronchoscopy include hemoptysis (occurs 10-25% of the time and does not exceed more than 2 tablespoons of coughed-up blood in twenty-four hours), epistaxis and fever (occurring in less than 10-25% of subjects). One death has been reported in the literature, which was attributed to excessive lidocaine administration.

Managing risk: Prior to the bronchoscopy, participant may be given an aerosolized lidocaine treatment by nebulizer or the nose, throat, and vocal cords will be sprayed with lidocaine to minimize coughing during the procedure. During the bronchoscopy, patients are placed on supplemental oxygen and monitored continuously with an oxygen saturation monitor as well as electrocardiogram. The topical anesthesia and sedation dosages are monitored, and limits set and adhered to closely. Research bronchoscopies will be done with subjects with a pre-bronchodilator FEV1 > 50% of predicted. Patients will be instructed to remain on their long-term asthma medication controllers prior to undergoing bronchoscopy. Pre- and post-bronchoscopy care will be provided in

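### The one planned safety call after bronchoscopy is set at both 24 hours and 1 week; the CT dose total is also wrong as written, and the lavage volume needs aligning

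*Combined protocol and SAP*

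**What the plan says.** **Call after bronchoscopy.** Under Enrollment, Study Visits & Procedures, Visit 3 is headed "follow up (1 week after visit 2". Its whole content is one telephone call with the coordinator, including a "review of interim medical history and medications and any AE's evaluated". In the Schedule of Events, the V3 column (week label 1+) places the follow-up call at "X (24 hours after bronchoscopy". The synopsis (Study Schedule) lists for Visit 3 only "a follow up phone call", with no time. The Visit 2 text lists no call of its own.

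**Call after MRI, for comparison.** All three places agree. The synopsis has "Approximately 24-hours after MRI, a follow up phone call", the Schedule of Events has "X (24 hours after MRI", and the Visit 1 text has "Participants will receive a follow up phone call approximately 24 hours after the MRI with the coordinator".

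**Bronchoscopy risks.** Item 7 of the Risk / Benefit Assessment gives "bleeding, bronchospasm, irregular heartbeat, shortness of breath, infection or pneumonia in approximately 1-5% of individuals with asthma". It also gives hemoptysis in 10-25%, and fever. The procedure description says that lower oxygen saturation is common for several hours after lavage.

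**CT dose.** The Chest SDCT entry and the SDCT safety item both state one scan, 4 mSv per scan for an adult of average weight, a study total of 8 mSv, and a comparator of 50 mSv. The section on recruitment and screening and the Schedule of Events confirm a single scan.

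**Lavage.** The Visit 2 text gives 90 mL per airway in two airways, 180 mL in all, and does not say whether this is instilled or returned. The procedure description gives three 40 mL aliquots, 120 mL instilled in each of the two airways, and has the returned volume measured separately.

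**The concern.** The call is the point of substance. Bronchoscopy is the most invasive step in the study, with lavage of two airways, up to 12 brushings and up to 12 biopsies under moderate sedation. It is followed by 25 minutes to 1 hour of observation. After that the plan has one contact, at two different times.

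Staff who follow the table have no planned adverse-event review after day 1, although infection and pneumonia are among the listed risks. Staff who follow the visit text have no planned contact before day 7, although the plan itself describes early desaturation, hemoptysis and fever. If different staff follow different pages, adverse events are collected over windows of different length, and the tallies that go to the DSMB are not comparable between participants.

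The CT figure is a risk statement that disagrees with its own inputs by a factor of two, and it is printed twice. The lavage figures would matter operationally if 90 mL were read as the volume to instil.

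**Working it through.** **1. Call timing: cross-reading**

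| Place | MRI call | Call after bronchoscopy |
|---|---|---|
| Synopsis, Study Schedule | 24 hours | one call, no time |
| Schedule of Events | 24 hours | 24 hours (V3 column) |
| Visit text | 24 hours (under Visit 1) | 1 week (Visit 3) |

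Could these be two separate calls? The 24-hour entry sits in the V3 column itself. The visit text lists the 24-hour MRI call under Visit 1 but lists nothing comparable under Visit 2. Each place therefore describes one call, and the times differ.

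- Gap: 7 x 24 - 24 = 144 hours.
- A 24-hour call alone leaves 7 - 1 = 6 days of the first week without a planned review.
- A 1-week call alone leaves no planned contact between discharge and day 7.
- Cost of having both: 50 participants x 1 additional call = 50 calls at most.

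**2. CT dose**

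Inputs: 1 scan, 4 mSv per scan, stated total 8 mSv, comparator 50 mSv.

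- Reproducing the stated total: 8 / 4 = 2 scans would be needed. The plan has one.
- Total from the plan's own inputs: 1 x 4 = 4 mSv.
- Against the comparator: 4 / 50 = 8%; 8 / 50 = 16%.

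**3. Lavage volume**

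Inputs: 3 aliquots of 40 mL per airway and 2 airways (procedure description); 90 mL per airway and 2 airways (Visit 2 text).

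- Procedure description: 3 x 40 = 120 mL per airway; 2 x 120 = 240 mL.
- Visit 2 text: 2 x 90 = 180 mL.
- If 90 mL is instilled: the difference is 30 mL per airway and 60 mL per participant, and 90 / 40 = 2.25 is not a whole number of aliquots.
- If 90 mL is the expected return: there is no conflict, and the implied recovery is 90 / 120 = 75%. It would have to include the first aliquot, because the pooled sample excludes that return and so comes from only 2 x 40 = 80 mL instilled.

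**The case against.** The strongest case on the other side is that these are wording slips with no statistical consequence. That is right as far as it goes: nothing here touches the sample size, the power statement or the comparison of fibrosis markers between fixed and reversible segments. It does not dispose of the call, because a safety contact with two times cannot be carried out as written.

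Other safeguards exist. There is observation in recovery, an escort is required, a participant in continuing difficulty would be hospitalized, an unscheduled visit is compensated, and a DSMB reviews adverse events. None of these is a planned later contact with every participant. They do mean that a reader should not infer that events in the uncovered days would go unrecorded. The 6 days count time without a scheduled review, not missed events. The 1-5% pools several complications, the procedure description gives at most 2-3%, and neither comes with onset times, so no number of affected events can be derived.

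One might settle the conflict by keeping only the 1-week call. That removes the contradiction but gives up the early contact, which the plan's own description of desaturation, hemoptysis and fever argues against. The documents do not say which time was intended. The week label 1+ for V3 fits 24 hours rather better than a week after a week-1 visit.

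On CT, it is tempting to read 8 mSv as the weight-adjusted dose for one scan in a cohort with BMI of at least 30. The text does not support this: it labels 8 mSv as the study total. It is fair to say that, on the stated inputs, the slip overstates exposure, which is the cautious direction. The consent pages are not available, so what participants are told cannot be judged.

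On lavage, a flat contradiction should not be inferred, since it depends on 90 mL meaning instilled volume. No text supports the return reading, but none excludes it. The procedure description is complete and self-consistent for an operator. Either volume is the same in both of a participant's airways, so using one or the other does not by itself bias the within-person contrast. No lavage endpoint per mL is named.

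**Conclusion.** The point stands and should be fixed. The only scheduled contact after bronchoscopy has two times, 144 hours apart, and neither alone covers both the early and the later post-procedure period. This rests on reading Visit 3 as one call, which all three places in the document support. The consequence is for safety follow-up and for consistent adverse-event collection; its size in events cannot be estimated from the documents.

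The CT total is wrong as written: the plan's own inputs give 4 mSv, not 8 mSv. The lavage volume is a minor point, conditional on what the 90 mL refers to. None of the three affects sample size, power or the planned fibrosis analysis.

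**What to change.** **Calls.** Schedule two calls after bronchoscopy for all participants, one at 24 hours and one at 1 week, each with adverse-event review. State them identically in the synopsis, the Schedule of Events and the visit text. Cost: wording changes and at most 50 additional short calls.

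**CT.** Correct the study total to 4 mSv in the Chest SDCT entry and in the SDCT safety item. If the sponsor expects a different dose in this cohort with BMI of at least 30, state that one figure as both the per-scan dose and the total. Cost: wording only.

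**Lavage.** Align the Visit 2 text with the procedure description, at 120 mL instilled per airway and 240 mL in total. If 90 mL is meant as expected return, label it so. Cost: wording only.
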